3.2 Screening/Run-In Period: 4 weeks

The Screening Period is 31 days. Patients using a documented stable dose of nasal mometasone at least 200 mcg/day, or an equivalent daily dose of another INCS, for at least 28 days before randomization will be asked to continue the dose for the duration of the study. For patients who are using an alternative INCS product other than MFNS prior to the screening visit, the investigator must switch the patient to MFNS at Visit 1. Patients will be asked to standardize their INCS to a regimen of mometasone furoate (NASONEX®) nasal spray (MFNS) of 2 actuations (50 mcg/actuation) in each nostril BID, total daily dose of up to 400 mcg, unless they are intolerant to BID INCS, in which case, they may remain on a stable dosage of mometasone of 2 actuations (50 mcg /actuation) in each nostril once daily, total daily dosage of 200 mcg.

Patients must use nasal mometasone at least 200 mcg/day, or equivalent, for at least 28 days before randomization, which can include days prior to screening with supportive documentation. Run-in can be 7-31 days with compliance determined in the week prior to randomisation using patient diary entries. If patients fail compliance requirements, they may undergo retraining with the patient diary and repeat the run-in period of 7 days.

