6.1 Screening (Visit 1), Study Day -31 to -1

The following assessments and procedures should be completed in the order given below, if possible:

- Collect signed and dated ICF, Health Insurance Portability and Accountability Act (HIPAA) Form, and Experimental Research Subject's Bill of Rights (if appropriate for that region).
- Receive a 6-digit patient number
- Review inclusion and exclusion criteria
- Record medical history and demographics
- Vital sign measurements
- Record height and body weight
- Review and record prior and concomitant medications
- CT Scan (only required for subjects that are enrolled at Study Sites that are approved and qualified to perform CT Scans)
- NCS assessment
- VAS-rhinosinusitis assessment
- SNOT-22 assessment
- TNSS assessment
- Nasal endoscopy and NPS scoring
- Spirometry (Baseline pulmonary function test) and reversibility testing if documentation of $\geq 12\%$ reversibility is not available in the prior 12 months
- Complete physical examination
- 12-lead ECG
- Hepatitis & HIV Screens
- Pregnancy test (Blood collection for pregnancy test for female patients of childbearing potential at Visit 1 then urine pregnancy tests at subsequent visits)
- Safety laboratory tests (hematology, serum chemistry, urinalysis)
- Dispense and instruct eligible patients on the proper use of the handheld device to capture NPIF, patient diary of symptoms (rhinorrhea etc), concomitant medication use.
- Sites may also provide MFNS for required concomitant use
- Dispense optional take-home rescue medications (albuterol/salbutamol) to asthma patients, if needed. Instruct patients to document the use of albuterol/salbutamol in their patient diary.

- AE review and recording

Screen failures should be recorded in the eCRF but they do not need to undergo all assessments listed for the Early Termination Visit. The Early Termination Visit assessments should be performed with patients if they withdraw from the study after randomization.

6.2 Baseline Visit (Visit 2), Study Day 1

The following assessments and procedures should be completed in the order given below, if possible:

- Review patient diary and NPIF data; retrain patient on proper diary use, if necessary
- Review and record prior and concomitant medication
- Vital sign measurement
- Record weight
- NCS assessment
- EQ-5D-5L questionnaire
- VAS-rhinosinusitis assessment
- SNOT-22 assessment
- TNSS assessment
- UPSIT assessment of smell
- Nasal endoscopy and NPS scoring

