7.8 Efficacy Assessments

7.8.1 Endoscopic Nasal Polyp Score

NPS is assessed by central video recordings of nasal endoscopy. The score (NPS) is the sum of left and right nostril scores, as evaluated by means of nasal endoscopy. NPS is graded based on polyp size as described in [Table 2](#) and depicted in the NPS figures below.

Suzhou Connect Biopharmaceuticals, Ltd

Protocol CBP-201-WW003

Investigational Drug: CBP-201

21 December 2021

Table 2: Endoscopic Nasal Polyp Score

Polyp Score	Polyp Size
0	No polyps
1	Small polyps in the middle meatus not reaching below the inferior border of the middle turbinate
2	Polyps reaching below the lower border of the middle turbinate
3	Large polyps reaching the lower border of the inferior turbinate or large polyps medial to the middle turbinate (i.e., reaching below the middle turbinate).
4	Large polyps causing complete obstruction of the inferior nasal cavity (i.e., touching the floor of the nose).

Nasal Polyp Scoring Figures

MT – middle turbinate; IT – inferior turbinate

Figure 1 Nasal Polyp Score of 0

[figure not shown]
[figure not shown]

Figure 2 Nasal Polyp Score of 1

Suzhou Connect Biopharmaceuticals, Ltd

Protocol CBP-201-WW003

Investigational Drug: CBP-201

21 December 2021

Figure 3 Nasal Polyp Score of 2

[figure not shown]

Figure 4 Nasal Polyp Score of 3

[figure not shown]
[figure not shown]

Figure 5 Nasal Polyp Score of 4

Note: Nasal endoscopy should be conducted at the end of the scheduled visits before the administration of study drug and preceded by local administration of anaesthetic drugs combined with a decongestant. Complete all assessments that might be affected by the procedure prior to application of the anaesthetic (i.e. UPSIT, SNOT-22, NCS, etc).

Standard video sequences will be available and sent to centralized reader. Centralized imaging data assessments and scoring by independent physician reviewer(s) for the imaging data will be performed for all endoscopies. At V1, the nasal endoscopy video must be sent for central reading and the results will be provided to the site. At Visit 2, if nasal endoscopy is performed (i.e. if V2 is >7 days after V1), the investigator will perform the nasal endoscopy and assess NPS to confirm eligibility. Thus, the patient's eligibility will be based on V1 central reading and, if performed, V2 local reading NPS score of ≥ 5 and ≥ 2 each side. The results of central reading from V2 onward will be available to sites after the study.

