Central reading of V2 will be used for primary endpoint analysis to compare with the Week 24 readings. Further details on nasal endoscopy will be provided to sites in a separate operational manual.

If Baseline Visit (Visit 2) is performed within 7 days of Screening Visit (Visit 1) the NPS score (central read) from the screening visit will be used to confirm eligibility, and the endoscopy will not be repeated at Visit 2 unless there were technical difficulties with the Visit 1 scoring.

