### 4.2 Definitions

#### Age at Baseline

Age will be calculated using the date of birth and date of the baseline visit as below:

Integer part of [(Date of Baseline Visit – Date of Birth) / 365.25]

Baseline

Unless otherwise specified, baseline is defined as the last non-missing value prior to the first dose of study drug. If time is not collected but the assessment is performed on the same day as the first dose of study drug, it would be considered as baseline.

Baseline Week

For weekly average analysis, baseline week is defined as 7 days prior to the baseline visit (Study day ranges from -7 to -1).

Change from Baseline

Change from baseline is defined as post-baseline value minus baseline value.

Study Day 1

Study day 1 is defined as the date of randomization for untreated randomized subjects or the date of first dose for treated subjects.

Study Day

Study Day will be calculated relative to the date of randomization for untreated randomized subjects and relative to the date of first dose for treated subjects.

If event is prior to the first dose, then study day is calculated as:

$$\text{Date of Event} - \text{Date of First Dose}$$

If event is after the first dose, then study day is calculated as:

$$\text{Date of Event} - \text{Date of First Dose} + 1$$

Duration of Treatment

Duration of Treatment (days) will be calculated as:

$$\text{Last Date of Dose} - \text{First Date of Dose} + 1$$

Treatment-Emergent Adverse Events

Treatment-emergent adverse events are defined as any adverse events occurred or worsen during the treatment-period, whether considered related to the treatment.

Where the AE start date is missing, adverse events will be assumed to be treatment-emergent, unless there is clear evidence (through comparison of partial dates) to suggest that the adverse event started prior to the first dose of study treatment.

Prior and Concomitant Medication

Prior and concomitant medication is defined as any medications that started before the first dose of study drug and stops on or after the first dose of study drug.

Prior Medication

Prior medication is defined as any medications that started and stopped before the first dose of study drug.

Concomitant Medication

Concomitant medication is defined as any medications that started on or after the first dose of study drug.

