**Table 3. Analysis Window for NPS, VAR-RS, SNOT-22, and TNSS**

Nominal Visit	Analysis Visit	Minimum Study Day	Maximum Study Day
Visit 2	Baseline	-7	-1
Visit 3	Week 1	1	8
Visit 4	Week 2	9	15
Visit 5	Week 4	23	29
Visit 7	Week 8	51	57
Visit 9	Week 12	79	85
Visit 11	Week 16	107	113
Visit 13	Week 20	135	141

Visit 15	Week 24 (End of Treatment)	163	169
Visit 17	Week 32 (End of Study)	219	225

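### SAP Table 3 gives the single-visit nasal polyp score the look-back windows of the diary averages, so on-schedule late endoscopies and the Day 1 baseline endoscopy miss their own analysis visit

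*SAP*

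**What the plan says.** SAP Section 4.3.1 assigns assessments to analysis visits by study day. Table 3 covers NPS, the rhinosinusitis visual analogue scale, SNOT-22 and TNSS, all collected at a single clinic visit. Three of its rows matter here:

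- Week 24: "Visit 15 Week 24 (End of Treatment) 163 169"
- Baseline: "Visit 2 Baseline -7 -1"
- Week 1: "Visit 3 Week 1 1 8"

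Table 4 gives the windows for weekly diary averages and has the same days at every visit the two tables share. Tables 1 (safety) and 2 (CT) instead give Week 24 a target of Day 169 and a range of 166 to 172.

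The protocol (Sections 6.4, 6.7, 6.11, 6.15 and 6.17) schedules post-baseline endoscopy at Weeks 2, 8, 16 and 24, each ± 3 days, and at Week 32 ± 5 days. Visit 2 is Study Day 1, and endoscopy precedes dosing. Protocol 7.8.1 states: "Central reading of V2 will be used for primary endpoint analysis to compare with the Week 24 readings". It omits the Visit 2 endoscopy when Visit 2 is within 7 days of Visit 1, unless the Visit 1 scoring had technical problems. Protocol 3.2 says of the interval between the visits: "Run-in can be 7-31 days with compliance determined in the week prior to randomisation".

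SAP Section 4.2 has a general rule: "Unless otherwise specified, baseline is defined as the last non-missing value prior to the first dose of study drug". It adds that a same-day assessment without a recorded time counts as baseline.

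SAP 4.15 withdraws formal testing but keeps descriptive summaries of the co-primary endpoints. SAP 4.11.2 defines these as Week 24 values and changes from baseline.

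**The concern.** A window that ends on the target day suits an average of the preceding week's diary entries. It does not suit one endoscopy that may properly take place up to three days after the target. Read literally, Table 3 leaves an on-schedule Week 24 endoscopy on Day 171 without an analysis visit, while a CT scan at the same visit counts as Week 24.

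The baseline row has a matching fault. It excludes the day of the baseline visit and assigns it to Week 1, a visit with no scheduled endoscopy. A patient with a longer run-in could have no NPS baseline, and so no change from baseline, or could have a pre-dose reading labelled as post-treatment.

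At stake is which NPS values enter the one efficacy summary of that endpoint that remains. If late attendance is related to the patient's condition, the Week 24 mean is also computed on a selected group.

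**Working it through.** **1. Where 163 to 169 comes from.** Target ± 3 gives 169 - 3 = 166 to 169 + 3 = 172, which does not match. A 7-day look-back gives 169 - 6 = 163 to 169, which matches exactly. All ten Table 3 rows equal the corresponding Table 4 rows.

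**2. Post-baseline endoscopy visits.** Each permitted protocol day was compared with the Table 3 rows.

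| Visit | Protocol days | Table 3 | Permitted days in no window |
|---|---|---|---|
| Week 2 | 12–18 | 9–15 | 16–18 (3 of 7) |
| Week 8 | 54–60 | 51–57 | 58–60 (3 of 7) |
| Week 16 | 110–116 | 107–113 | 114–116 (3 of 7) |
| Week 24 | 166–172 | 163–169 | 170–172 (3 of 7) |
| Week 32 | 220–230 | 219–225 | 226–230 (5 of 11) |

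The shares are 3/7 = 42.9% at each on-treatment visit (12 of 28 in total) and 5/11 = 45.5% at Week 32. At Week 24, Days 163 to 165 are accepted although they are outside tolerance. At Week 1, permitted Days 9 to 11 fall in the Week 2 row, but no endoscopy is due then.

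Section 4.3.1 has no fallback for a scheduled assessment outside every window. Its closest-to-target rule works only within a window and needs a target day, which Tables 3 to 5 do not give.

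**3. Baseline.** By the SAP's study-day rule, a Visit 1 held g days before first dose has study day -g, and Visit 2 has study day 1. For g = 7 the endoscopy is normally not repeated, and Visit 1 (Day -7) lies in the row. For g = 8 to 31 the scheduled readings are on Day -g (Day -8 or earlier) and Day 1, and neither lies in -7 to -1. So 24 of the 25 permitted run-in lengths leave the row empty. This counts lengths, not patients.

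**4. Size at Week 24.** The documents give no late-visit rate, so the late share f is an assumption. The value 3/7 corresponds to visits spread evenly over the seven permitted days. The standard error of a mean is multiplied by 1/√(1 - f) at any sample size:

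- f = 0.10: 1/√0.90 = 1.054, up 5%
- f = 0.25: 1/√0.75 = 1.155, up 15%
- f = 3/7: 1/√0.571 = 1.323, up 32%

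**5. Illustration for the withdrawn test only.** The inputs are those of SAP 4.14: difference 1.3, SD 2.1, two-sided alpha 0.05, 41 per group. The normal approximation reproduces the stated 80% (0.800). The two-sample t-test, with noncentrality 1.3/(2.1·√(2/n)) and 2n - 2 degrees of freedom, gives 79.1%. With n = 41(1 - f) = 36.9, 30.8 and 23.4, power is 74.6%, 66.6% and 54.5%. These are completers-only figures; the repeated-measures model would have recovered part of the loss.

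**The case against.** The strongest objection is that little now depends on this. Testing, sensitivity and subgroup analyses are gone, SAP 4.11.2 defines the co-primary summary at Week 24 only, and other efficacy assessments are merely listed. That is right about scope: the loss that clearly reaches a planned output is 3 of 7 days at Week 24, plus the baseline. The other weeks show the same fault but may reach no summary, and the power figures describe a test that will not be run. Every reading also stays in the by-subject listing.

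On baseline, SAP 4.2 defines a separate baseline week of Days -7 to -1 expressly for weekly averages. Together with Protocol 7.8.1, this shows that the Day 1 endoscopy was probably meant to be the NPS baseline. That is a fair reading of intent. However, the general rule in 4.2 yields wherever something else is specified, and Table 3 specifies something else for NPS by name. Two programmers could follow the SAP and obtain different baselines.

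Finally, the SAP never says that out-of-window readings are discarded, and its tables carry a nominal-visit column, so a late Visit 15 endoscopy might be kept under its nominal label. It might, but no rule says so. The only written allocation is by study day, and correct output should not depend on setting a table aside.

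**Conclusion.** The concern holds. Table 3 applies diary look-back windows to a single-visit measure, contrary to the protocol's visit tolerance and to SAP Tables 1 and 2. Taken literally, it excludes 3 of the 7 permitted Week 24 days from the NPS summary. It also leaves the baseline row without a scheduled NPS reading whenever Visit 2 is more than 7 days after Visit 1. A late endoscopy costs that visit's record, not necessarily the whole patient.

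The day counts follow from the documents alone. The baseline count assumes endoscopies only at Visits 1 and 2, with Visit 2 on Day 1. The 5% to 32% rise in standard error rests on assumed late-visit shares of 10% to 43%. No hypothesis test is affected, but the table should be corrected because a retained co-primary summary depends on it.

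**What to change.** In Table 3, use windows that contain the full protocol tolerance: ± 3 days on treatment and ± 5 days at Week 32. Add the target day that the closest-to-target rule needs. The post-baseline rows of Table 1 already do both (Week 24 = 166 to 172). Make the same change, with ± 5 days at Weeks 28 and 32, to any single-visit measure governed by Table 5. That table does not list its parameters, so the SAP should name them.

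Align the NPS baseline row with SAP 4.2 and Protocol 7.8.1: a pre-dose Day 1 endoscopy is baseline, Visit 1 serves when endoscopy is not repeated at Visit 2, and Week 1 starts on Day 2. State which rule governs if they differ. Keep the look-back windows for the diary averages in Table 4.

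The cost is SAP wording and reprogramming of visit windows, with no new data. The downside is slightly more spread in assessment timing, up to 3 days after target on treatment.

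This does not settle early-termination endoscopies that fall between visits. Table 3 leaves 112 of Days 1 to 169 uncovered (66%), and ± 3 windows on the same rows leave 116 (69%). Those readings should be summarised separately, for example as the last on-treatment NPS, and not relabelled as Week 24.

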**Table 4. Analysis Window for Efficacy Parameters – Weekly average**

Nominal Visit	Analysis Visit	Minimum Study Day	Maximum Study Day
Visit 2	Baseline	-7	-1
Visit 3	Week 1	1	8
Visit 4	Week 2	9	15
Visit 5	Week 4	23	29
Visit 6	Week 6	37	43
Visit 7	Week 8	51	57
Visit 8	Week 10	65	71
Visit 9	Week 12	79	85
Visit 10	Week 14	93	99
Visit 11	Week 16	107	113
Visit 12	Week 18	121	127
Visit 13	Week 20	135	141
Visit 14	Week 22	149	155
Visit 15	Week 24 (End of Treatment)	163	169
Visit 16	Week 28	191	197
Visit 17	Week 32 (End of Study)	219	225

**Table 5. Analysis Window for Other Efficacy Parameters**

Nominal Visit	Analysis Visit	Minimum Study Day	Maximum Study Day
Visit 2	Baseline	-7	-1
Visit 3	Week 1	1	8
Visit 4	Week 2	9	15
Visit 5	Week 4	23	29
Visit 6	Week 6	37	43
Visit 7	Week 8	51	57
Visit 8	Week 10	65	71
Visit 9	Week 12	79	85
Visit 10	Week 14	93	99
Visit 11	Week 16	107	113
Visit 12	Week 18	121	127
Visit 13	Week 20	135	141
Visit 14	Week 22	149	155

Visit 15	Week 24 (End of Treatment)	163	169
Visit 16	Week 28	191	197
Visit 17	Week 32 (End of Study)	219	225

If more than one assessment is available within the same analysis visit, the assessment with closest study day to the target study day will be reported for the analysis window. If two observations exist with the same distance to the target study day, then the first observation will be used.

Unscheduled visit will not be used in the analysis if scheduled visit is available. Unscheduled visit will be used in the analysis only if scheduled visit is not available.

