Blood Sample for ADA, Nab ^p		X			X				X							X		X	X
Study Drug SC Administration ^q		X		X	X	X	X	X	X	X	X	X	X	X	X				
Dispense rescue medication and MFNS as needed ^r	X	X	X	X	X	X	X	X	X	X	X	X	X	X	X				
Assess Injection Site(s) ^s		X	X	X	X	X	X	X	X	X	X	X	X	X	X	X	X	X	X
Adverse Events	X	X	X	X	X	X	X	X	X	X	X	X	X	X	X	X	X	X	X

Abbreviations: ADA = antidrug antibodies; AE = adverse event; CT = computed tomography; D = Day, ECG = electrocardiogram; EOS = End-of-Study; EOT = End-of-Treatment; EQ-5D-5L = European quality of life questionnaire; FEV₁ = forced expiratory volume in the first second of expiration; HBcAb = hepatitis B core antibody; HCVAb = hepatitis C virus antibody; HBsAg = hepatitis B surface antigen; LABA = long-acting β -agonist; NAb = neutralizing antibody; NCS = Nasal Congestion Score; NPS = Nasal Polyp Score; NPIF = Nasal peak inspiratory flow; PD = pharmacodynamic(s); PK = pharmacokinetic(s); SABA = short-acting β -agonists; SC = subcutaneous; SNOT-22 = 22-item Sinonasal Outcome Test; TNSS = Total Nasal Symptom Score; UPSIT = University of Pennsylvania Smell Identification Test; V = visit; VAS-RS = Visual Analogue Scale for Rhinosinusitis; VS = vital signs; W = Week.

Footnotes:

- a. The screening period to collect baseline data and determine a patient's eligibility is 31 days in duration and begins when the ICF is signed.
- b. Vital signs include body temperature, respiratory rate, blood pressure, and heart rate. VS should be recorded predose for all treatment visits. On D1 (V2), W2 (V4), and W4 (V5), VS should be recorded hourly during the 2hour postdose monitoring period. On W6 (V6) and beyond, VS should be recorded at 30 minutes postdose. During the post-treatment Follow-Up Period, VS are to be recorded once during each visit. Vital signs may be modified if adapted to telemedicine or home health visits where continuous monitoring may not be possible.
- c. A complete physical examination will be performed, which assesses the following: general appearance, skin, eyes/ears/nose/throat, thyroid, head and neck, cardiovascular system, respiratory system, abdomen, fundoscopy (optional), extremities, lymph nodes, musculoskeletal, and nervous system.
- d. A brief physical examination will include an assessment of general appearance, eyes, lungs, and lymph nodes. Physical exams may be modified if adapted to telemedicine or home health visits.

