### **Footnotes:**

- a. The screening period to collect baseline data and determine a patient's eligibility is 31 days in duration and begins when the ICF is signed.
- b. Vital signs include body temperature, respiratory rate, blood pressure, and heart rate. VS should be recorded predose for all treatment visits. On D1 (V2), W2 (V4), and W4 (V5), VS should be recorded hourly during the 2-hour postdose monitoring period. On W6 (V6) and beyond, VS should be recorded at 30 minutes postdose. During the post-treatment Follow-Up Period, VS are to be recorded once during each visit. Vital signs may be modified if adapted to telemedicine or home health visits where continuous monitoring may not be possible.
- c. A complete physical examination will be performed, which assesses the following: general appearance, skin, eyes/ears/nose/throat, thyroid, head and neck, cardiovascular system, respiratory system, abdomen, fundoscopy (optional), extremities, lymph nodes, musculoskeletal, and nervous system.
- d. A brief physical examination will include an assessment of general appearance, eyes, lungs, and lymph nodes. Physical exams may be modified if adapted to telemedicine or home health visits.
- e. The Nasal Congestion Score should be captured in the patient diary but may be captured by an alternative manner (ie, paper) if the device fails between clinic visits.
- f. If V2 is performed within 7 days of V1, then NPS (central read) from V1 will be used to confirm eligibility, and the endoscopy will not be repeated at V2. For more details see section 7.8.1 Endoscopic Nasal Polyp Score.
- g. Spirometry, including FEV1, forced vital capacity, and peak expiratory flow, will be performed only for patients with asthma. Due to diurnal variation of lung function it is important that all spirometry assessments are performed preferably after 7:00 hours and no later than 11:00 hours. Prior to spirometry assessments, twice-daily LABA therapies, including combination therapies, should be withheld 12 hours, once-daily therapies containing LABA or long-acting muscarinic antagonists should be withheld for  $\geq$  24 hours, and SABAs should be withheld  $\geq$  6 hours. Reversibility of lung function will be tested if a medical history record of  $>12\%$  reversibility (improvement in FEV1) cannot be demonstrated within the previous 12 months.
- h. Hepatitis screen: For more details see section 7.6.

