**Table 1. Analysis Window for Safety Parameters**

Nominal Visit	Analysis Visit	Target Study Day	Minimum Study Day	Maximum Study Day
Visit 2	Baseline	1	-30	1
Visit 3	Week 1	8	2	11
Visit 4	Week 2	15	12	18
Visit 5	Week 4	29	26	32
Visit 6	Week 6	43	40	46
Visit 7	Week 8	57	54	60
Visit 8	Week 10	71	68	74
Visit 9	Week 12	85	82	88
Visit 10	Week 14	99	96	102
Visit 11	Week 16	113	110	116
Visit 12	Week 18	127	124	130
Visit 13	Week 20	141	138	144
Visit 14	Week 22	155	152	158
Visit 15	Week 24 (End of Treatment)	169	166	172
Visit 16	Week 28	197	192	202
Visit 17	Week 32 (End of Study)	225	220	230

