#### 4.12.5 Vital Signs

Descriptive summaries of actual values and changes from baseline at each visit will be summarized for temperature, systolic blood pressure, diastolic blood pressure, heart rate, and respiratory rate by treatment and overall. Baseline of vital signs is defined as pre-dose at Baseline visit. By-subject listing of vital sign parameters will also be provided.

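### Read literally, SAP 4.3.1 and 4.12.5 leave scheduled post-dose vital signs out of the summary tables whenever the pre-dose reading is present

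*SAP*

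**What the plan says.** **Collection.** Footnote b to the schedule of assessments (Protocol Table 1, repeated in SAP 3.2) sets three requirements:
- Before each injection: "VS should be recorded predose for all treatment visits"
- After the injection, at the first three dosing visits: "On D1 (V2), W2 (V4), and W4 (V5), VS should be recorded hourly during the 2-hour postdose monitoring period"
- After the injection, at the ten later dosing visits: "On W6 (V6) and beyond, VS should be recorded at 30 minutes postdose"

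**Selection.** The rules that close SAP 4.3.1 deal with several assessments falling in one analysis visit: "the assessment with closest study day to the target study day will be reported for the analysis window". For equal distance: "If two observations exist with the same distance to the target study day, then the first observation will be used". Distance is counted in days. Neither clock time nor planned time point is mentioned.

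**Windows.** "Table 1. Analysis Window for Safety Parameters" is the table that covers vital signs. Its Baseline window runs from Day -30 to Day 1, and Week 1 starts at Day 2. No visit is split into pre-dose and post-dose.

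**Summaries.** SAP 4.12.5 says: "Descriptive summaries of actual values and changes from baseline at each visit will be summarized for temperature, systolic blood pressure", and continues with the other vital signs, by treatment and overall. It gives no time point within a visit. Protocol 9.6 also works by treatment group and visit. SAP 4.12.5 separates pre-dose from post-dose in only one place: "Baseline of vital signs is defined as pre-dose at Baseline visit". It also plans a by-subject listing.

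**The concern.** The post-dose readings are the only scheduled vital-sign measurements taken after an injection. If the selection rule is programmed as written, they are collected but never summarised by arm. Every row for a dosing visit then shows values taken before that visit's injection.

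Vital signs are a named safety endpoint (SAP 3.3.1.6), and SAP 4.15 turns the remaining analysis towards safety after early termination. No other vital-sign output makes up for the gap. ECGs have a separate summary of abnormal findings (SAP 4.12.6) and laboratory tests have shift tables of toxicity grade (SAP 4.12.4). Vital signs have only the by-visit descriptives and a listing. A modest post-injection shift in blood pressure, heart rate or temperature that differed between arms, without leading to reported adverse events, would be visible only to someone reading listings patient by patient.

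**Working it through.** The documents state no figure on this point, so the check is a count of the schedule followed by a literal application of the rule.

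**1. Scheduled readings for one completer, Baseline to Week 32.** Hourly over 2 hours is read as two readings (1 h and 2 h); this is an assumption.

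| Visits | Number of visits | Pre-dose | Post-dose | Single, no dose |
|---|---|---|---|---|
| Day 1, Weeks 2 and 4 | 3 | 3 | 3 × 2 = 6 | – |
| Weeks 6 to 24, every 2 weeks | 10 | 10 | 10 × 1 = 10 | – |
| Weeks 1, 28 and 32 | 3 | – | – | 3 |
| Total | 16 | 13 | 16 | 3 |

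All readings: 13 + 16 + 3 = 32.

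**2. Distance to target.** For a reading on study day d with target t, distance = |d − t|. Readings taken on the same day have the same d. Example: a Week 6 visit (target Day 43) held on Day 45 gives |45 − 43| = 2 for both the pre-dose and the 30-minute reading. They tie, and the first observation is the pre-dose one.

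**3. Result over the whole schedule.**
- With visits on target, 2 days late or 3 days early, the rule keeps 16 of 32 readings, one per analysis visit: 13 pre-dose and 3 single. It keeps 0 of the 16 post-dose readings in each case.
- With the Week 12 pre-dose reading missing, 31 readings remain. The rule keeps 16, of which 1 is post-dose. That 30-minute value would sit in the Week 12 row, unlabelled, beside other patients' pre-dose values.

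**4. Does the rule reach vital signs?** It needs a target study day. Only Table 1 (safety) and Table 2 (CT) of SAP 4.3.1 have that column; Tables 3 to 5 do not. Safety parameters are therefore where the rule can be run directly as written.

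**5. Day 1.** Post-dose readings on Day 1 fall inside the Baseline window, which ends that day, while SAP 4.12.5 defines baseline as pre-dose. Week 1 cannot take them because it starts at Day 2. They have no post-baseline row whatever the tie-break is taken to mean.

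**6. With summaries by visit and planned time point,** all 16 post-dose readings enter the tables.

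**The case against.** The strongest objection is that the rule was not written for this case. It speaks of distance to a target day and stands beside the visit windows and the rule on unscheduled visits. Its natural use is to choose between visits on different days, such as one 2 days early and one 2 days late. SAP 4.12.5 shows that its authors knew vital signs have time points within a visit, and it nowhere says that post-dose values are excluded. A sensible programmer might add time points unprompted. This stands as an account of likely intent. It does not remove the problem: SAP section 1 presents the document as the specification for programming, the rule is triggered whenever an analysis visit holds more than one assessment, and no exception is given.

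A reader might go further and infer that the SAP deliberately discards every post-dose reading, and with it the only planned check on acute effects of injection. The documents do not support that:
- Patients are observed for 2 hours or 30 minutes after dosing, and the new injection site is assessed before release.
- Adverse events are collected throughout. Anaphylaxis is an event of special interest, and the Protocol 8.6 definition includes blood-pressure criteria. Adverse events and events of special interest are tabulated (SAP 4.12.2 and 4.12.3).
- All vital signs are listed by subject, so no reading is lost.
- A post-dose value is tabulated when the pre-dose one is missing.
- The tables are not confined to dosing visits; Weeks 1, 28 and 32 have their own rows.

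Adverse event tables capture reported events, however. They do not show average shifts by arm, and listings do not compare arms. It is also fair to say that the vital-sign tables are descriptive, so no test or trial conclusion turns on them.

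**Conclusion.** The point holds as a defect in the specification of a safety output. Followed as written, SAP 4.3.1 and 4.12.5 bring 0 of up to 16 scheduled post-dose sets per completer into a summary table when all pre-dose readings are present, and mix time points without a label when one is missing. The lack of a post-baseline row for Day 1 does not depend on how the tie-break is read.

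The count of 16 assumes two readings in each 2-hour period, a patient who completes all 13 dosing visits, and no changes for telemedicine or home visits, which footnote b allows. It is a maximum. Scaling it to the planned enrolment (147 × 16 = 2,352) gives a ceiling that early termination puts out of reach, so it should not be used as the size of the problem. The consequence is that post-dose changes in vital signs by arm go unsummarised. The documents do not show that acute safety as a whole goes unexamined.

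**What to change.** 1. In SAP 4.3.1, state that the one-record-per-visit rule applies within each planned time point, so that it chooses between repeat assessments of the same kind and does not choose between pre-dose and post-dose.
2. In SAP 4.12.5, summarise vital signs by visit and time point: pre-dose, 1 h and 2 h on Day 1, Week 2 and Week 4; pre-dose and 30 min from Week 6. Label the time point in every row.
3. Show the Day 1 post-dose readings as their own post-baseline rows, with the pre-dose reading as baseline, as SAP 4.12.5 already defines it.

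Change from the same visit's pre-dose value would be a useful extra, but neither document promises it and it is optional.

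The cost is a few sentences in the SAP and extra table rows. The schedule already collects the data, and no study procedure changes.
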